6.1.3.2.3. Child-Turcotte-Pugh (CTP) Score and MELD Score

Laboratory assessment data will be used to determine the CTP score and MELD score. CTP will be calculated as a summation of all points assigned as shown in Table 6-1.

Table 6-1. Child-Turcotte-Pugh Score Calculations

Parameter	Points Assigned		
	1	2	3
Ascites	Absent	Slight	Moderate

Total Bilirubin	< 2 mg/dL (< 34.2 micromol/liter)	2 - 3 mg/dL (34.2 - 51.3 micromol/liter)	> 3 mg/dL (> 51.3 micromol/liter)
Albumin	> 3.5 g/dL (> 35 g/liter)	2.8 - 3.5 g/dL (28 - 35 g/liter)	< 2.8 g/dL (< 28 g/liter)
Prothrombin Time (Seconds over control, PT) OR International normalized ratio (INR)*	< 4 < 1.7	4 – 6 1.7 – 2.3	> 6 > 2.3
Encephalopathy	None	Grade 1 - 2	Grade 3 - 4

* INR is chosen for this study’s CTP calculation per eCRF.

A total CTP score of 5-6 is considered grade A (compensated), 7-9 is grade B (significant functional compromise/decompensated), and 10-15 is grade C (decompensated). A missing CTP score/cirrhosis status not available will be displayed as “Unknown” grade category in summaries. The proportion of participants in each CTP score category (A [5-6], B [7-9] and C [10-15]) will be summarized by visit for each treatment group. A shift table of CTP category by treatment group will be provided as well. By-participant, by-visit listing of CTP score results will be provided by participant ID number in chronological order.

MELD score will be calculated at each visit. Table with descriptive statistics (n, mean, SD, median, Q1, Q3, minimum, and maximum) for MELD score and change from baseline by visit for each treatment group will be provided. A shift table for MELD score category (\geq or <15) at each postbaseline visit from baseline will also be provided by treatment group. MELD score results will be listed by participant ID number and visit.

The MELD score will be calculated using the following formula:

$$10 \times \{[0.957 \times \text{Ln}(\text{Scr})] + [0.378 \times \text{Ln}(\text{Tbil})] + [1.12 \times \text{Ln}(\text{INR})] + 0.643\},$$

Where Scr = serum creatinine (in mg/dL), Tbil = Total Bilirubin (in mg/dL), INR = international normalized ratio, and Ln = natural log. If any lab value was less than 1.0, then it will be set to 1.0 in the calculation. If the participant received dialysis at least twice in the past week, then Scr will be set to 4.0 mg/dL in the above formula. The result will be rounded to the nearest whole number.

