### 6.3.9. MELD Score and Child-Turcotte-Pugh Score

Model for End-Stage Liver Disease (MELD) Score and Child-Turcotte-Pugh (CTP) data will be calculated at each visit.

For the components of the MELD score and the components of the CTP score which are based on laboratory values, the data will be obtained from the central laboratory, and the scores will be calculated within the clinical database.

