1.3. Sample Size and Power

No formal power or sample size calculations were applied.

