7.2. Others – Prior and Concomitant Medications

Participants will not receive any antiviral therapy for HCV infection while participating in this Registry. If a participant requires HCV antiviral therapy, they will be discontinued from the Registry. There are no other concomitant medications which would preclude participants from participating in this Registry. The concomitant medication records collected will be listed.

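### CTP and MELD use measured INR with no rule for vitamin K antagonists, so a drug effect can move the shift tables and the baseline CTP class

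*SAP*

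**What the plan says.** Protocol 6.3.9 says that, for the laboratory components of both scores, "the data will be obtained from the central laboratory, and the scores will be calculated within the clinical database". SAP 6.1.3.2.3 repeats the source: "Laboratory assessment data will be used to determine the CTP score and MELD score". Of the two coagulation options in SAP Table 6-1, the footnote settles on one: "INR is chosen for this study’s CTP calculation per eCRF". MELD takes the natural log of the same INR.

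The planned outputs are CTP category proportions by visit, a CTP shift table, MELD values and change from baseline, and "A shift table for MELD score category" cut at 15. All of these sit under SAP 6.1.3.2, the primary endpoint on liver disease progression or regression. SAP 3.2 and 6.1.3.2.1 also use CTP class at entry to split a further set of liver-event tables.

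On medication, Protocol 5.2 bars only HCV antivirals, and neither exclusion criterion in Protocol 4.2 names anticoagulants. SAP 7.2 says: "There are no other concomitant medications which would preclude participants from participating in this Registry. The concomitant medication records collected will be listed". Nothing links those records to CTP or MELD.

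The same SAP section does adjust one input for treatment: recent dialysis overrides the measured creatinine. INR has no counterpart.

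**The concern.** In a participant on a vitamin K antagonist, INR largely reflects the drug and no longer isolates hepatic synthetic function. The formulas cannot tell the difference. If the drug starts after entry, the scores worsen. If it stops, they improve. If INR drifts across 1.7 or 2.3 while the participant stays on the drug, CTP points move in either direction. None of these changes need involve the liver.

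Two sets of outputs are exposed. The first is the CTP and MELD summaries and shift tables, which are part of the display for a primary endpoint. SAP 6.1.3.2.3 describes class B in terms of decompensation, so a compensated participant on the drug can be reported as decompensated. The second is baseline CTP class. A participant on the drug at entry can be placed in too severe a class and carry that label into the by-CTP tables for first liver event, De Novo HCC, decompensation, transplant and all-cause death. The disposition, demographic, baseline and varices tables are split by the same class.

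**Working it through.** The plan gives no figure to reproduce: "No formal power or sample size calculations were applied". The check applies the SAP's own scoring rules and varies INR alone.

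**Inputs from SAP 6.1.3.2.3**
- CTP points for INR: below 1.7 = 1; 1.7 to 2.3 = 2; above 2.3 = 3.
- CTP classes: A 5-6, B 7-9, C 10-15.
- MELD = 10 × {0.957 ln(Scr) + 0.378 ln(Tbil) + 1.12 ln(INR) + 0.643}. Inputs below 1.0 are set to 1.0, and the result is rounded to a whole number.

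**Assumption, not in the documents:** INR of 1.0-1.4 off the drug and 2.0-3.0 on it, with 1.7 and 2.3 also shown because they are the CTP cut-points.

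**CTP, starting from INR below 1.7**
- INR 1.7-2.3 adds 1 point: 5 → 6 (stays A), 6 → 7 (A to B), 9 → 10 (B to C).
- INR above 2.3 adds 2 points: 5 → 7 and 6 → 8 (both A to B); 8 → 10 and 9 → 11 (both B to C).
- Stopping the drug reverses each move.

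**MELD with creatinine and bilirubin at the floor:** MELD = 6.43 + 11.2 × ln(INR)

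| INR | Raw | Rounded |
|---|---|---|
| 1.0 | 6.43 | 6 |
| 1.7 | 12.37 | 12 |
| 2.0 | 14.19 | 14 |
| 2.3 | 15.76 | 16 |
| 2.5 | 16.69 | 17 |
| 3.0 | 18.73 | 19 |

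Rounding to 15 needs a raw value of at least 14.5. That gives INR ≥ exp((14.5 − 6.43)/11.2) = exp(0.7205) = 2.06. With bilirubin at 1.5 mg/dL the base is 6.43 + 3.78 × ln(1.5) = 7.96, and the crossing falls to exp((14.5 − 7.96)/11.2) = 1.79.

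**Change from baseline.** The smallest drug-only rise over the assumed range is 11.2 × ln(2.0/1.4) = 4.0 raw MELD points. The largest is 11.2 × ln(3.0/1.0) = 12.3. If the flagged scores are left out, the drug contributes no change.

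**Study-level size.** Anticoagulant use, the INR distribution on the drug and the number in class A are all absent from the documents. Purely for scale, assume that 2-4% of class A participants are on such a drug at a visit and that half of them have INR above 2.3. Then 0.5 × 2% to 0.5 × 4% = 1-2% of class A would be scored as B at that visit. This is a share misclassified, not a shift rate: someone on the drug throughout is misplaced at baseline and may show no shift at all.

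**The case against.** The strongest reply concerns reach. A reader might infer that starting or stopping the drug is counted as a progression or regression event. It is not. The progression events in SAP 6.1.3.2.1 are a fixed list of clinical events, transplant and liver-related death, with no CTP or MELD change among them. No threshold on either score is defined as progression anywhere, and no hypothesis is tested. A reader might also infer that every Kaplan-Meier table is affected. SAP 6.1.3.2.1 first gives those tables by treatment group, and the by-CTP versions are an additional set. Nor does every user cross both cut-points. A CTP 5 participant with INR of 1.7-2.3 stays in class A, and at the laboratory floor MELD stays below 15 until INR is about 2.06.

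The other evidence on progression or regression (the event analyses, FibroTest, ELF, FIB-4, APRI and elastography) does not list INR as an input. INR, bilirubin, albumin, CTP, MELD and medications are all listed by participant, so a careful reader could spot an isolated INR rise.

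All of that stands, and it limits the point. It does not remove it. Listings do not correct the summary and shift tables, and SAP 3.6.2 keeps all data with no sensitivity analysis for outliers. The grouping variable is affected whether or not events are.

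Replacing on-drug INR with the last pre-drug value in the main tables also draws a fair objection. A value carried for years could hide real deterioration, and it would depart from the general no-imputation convention in Protocol 8.3 and SAP 3.6.1.

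**Conclusion.** The point holds in a limited form. Under the SAP's rules, INR raised by a vitamin K antagonist can by itself add 1 or 2 CTP points. Over the assumed INR range it can add about 4 to 12 raw MELD points. Either can move a participant across the A/B, B/C or MELD 15 boundaries. The exposed outputs are the CTP category summaries and shift table, the MELD change and shift tables, and the baseline CTP split.

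The stronger readings, that Kaplan-Meier events are created or that the drug accounts for a large part of the observed shifts, are not supported. The event list excludes both scores, and the documents give neither the number of users nor a true shift rate. The treatment-group Kaplan-Meier tables and the total columns of the by-CTP tables are unchanged. The per-participant arithmetic follows from the SAP, while the on-drug INR range and any study-level percentage are assumptions.

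**What to change.** Keep the planned tables as the main analysis and add to SAP 6.1.3.2.3:

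- Flag each visit on a vitamin K antagonist, using the medication records collected, and show the flag in the CTP and MELD listings.
- Add a sensitivity version of the CTP and MELD summaries and shift tables that leaves out flagged scores.
- Add a sensitivity version of the by-baseline-CTP event tables that leaves out participants flagged at baseline.
- Where medication data are incomplete, query every record with INR of 1.7 or more, whatever the bilirubin and albumin.

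The query matters because neither the Protocol visit lists and Appendix 2 nor SAP 12.2 schedules medication collection, so the completeness and dating of the records are unknown. Restricting it to participants with minimum-point bilirubin and albumin would miss many with CTP 6 and those in classes B and C. Even the wider query has a gap. With bilirubin at 2.0 mg/dL and creatinine at the floor, MELD reaches 15 at INR of about 1.63, below the query limit.

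The cost is a little more programming, a short query list and a few fewer scores in the sensitivity tables. Capture remains incomplete if the medication records are. No clinical rule changes. SAP section 1 already provides for changes after finalization to be documented in the CSR.

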3.6.2. Outliers

Outliers will be identified during the data management and data analysis process, but no sensitivity analyses will be conducted. All data will be included in the data analysis.

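### The MELD rule fixes creatinine at 4.0 mg/dL on dialysis but sets no upper limit off dialysis, so above 4.0 mg/dL starting dialysis is scored as an improvement

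*SAP*

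**What the plan says.** SAP section 6.1.3.2.3 defines MELD as 10 × (0.957 ln Scr + 0.378 ln Tbil + 1.12 ln INR + 0.643), with creatinine and bilirubin in mg/dL. Three rules accompany the formula:

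- Lower bound: "If any lab value was less than 1.0, then it will be set to 1.0 in the calculation".
- Dialysis: "If the participant received dialysis at least twice in the past week, then Scr will be set to 4.0 mg/dL in the above formula".
- Rounding: "The result will be rounded to the nearest whole number".

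No upper bound is given for creatinine off dialysis, and none can be borrowed from elsewhere. SAP section 3.6.2 on outliers says "All data will be included in the data analysis". SAP section 3.7 deals only with results beyond an assay's quantitation limits. Protocol section 6.3.9 has no MELD formula; for the laboratory components it says "the data will be obtained from the central laboratory, and the scores will be calculated within the clinical database".

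The SAP plans descriptive statistics "for MELD score and change from baseline by visit for each treatment group will be provided", including mean, SD, minimum and maximum. It also plans a shift table at a MELD of 15, which "at each postbaseline visit from baseline will also be provided by treatment group", and a listing by participant and visit.

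**The concern.** A severity score should not fall because a participant has started renal replacement. The SAP gives dialysed participants a fixed creatinine of 4.0 mg/dL, yet lets an undialysed participant enter the formula with any higher value. Above 4.0 mg/dL the two rules rank the same participant as less ill on dialysis than off it, and moving between the two states changes the score in the wrong direction. This is an inconsistency within the SAP's own rules and needs no outside MELD standard to see.

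MELD is one of the laboratory measures placed under the primary progression or regression endpoint (SAP section 6.1.3.2). The registry enrols participants with decompensated disease, and hepatorenal syndrome is a listed progression event, so creatinine above 4.0 mg/dL is plausible. A programmer following the text literally would apply no cap. One such participant could supply the reported maximum MELD or the most favourable change in a treatment group.

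**Working it through.** The documents contain no worked MELD value to reproduce, so the check evaluates the SAP formula directly.

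**Inputs from SAP section 6.1.3.2.3.** Creatinine coefficient 10 × 0.957 = 9.57 per unit of ln(Scr); constant 10 × 0.643 = 6.43; floor 1.0; dialysis value 4.0 mg/dL; rounding to a whole number; shift-table cut at 15.

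**Assumed inputs.** Creatinine of 1 to 12 mg/dL, and bilirubin and INR held fixed across the two visits. The main example puts both at 1.0, where their log terms vanish.

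**Step 1: change on starting dialysis.** The bilirubin and INR terms cancel, leaving

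Δ = 9.57 × ln(4.0/Scr).

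This is positive below 4.0 mg/dL, zero at 4.0 and negative above.

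**Step 2: score on dialysis, bilirubin and INR at 1.0.** 9.57 × ln 4 + 6.43 = 13.27 + 6.43 = 19.70, which rounds to 20.

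**Step 3: scores off dialysis, same bilirubin and INR.**

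| Creatinine off dialysis (mg/dL) | Unrounded MELD | Rounded MELD | Rounded MELD on dialysis | Change, rounded | Change, unrounded |
|---|---|---|---|---|---|
| 1 | 6.43 | 6 | 20 | +14 | +13.27 |
| 2 | 13.06 | 13 | 20 | +7 | +6.63 |
| 3 | 16.94 | 17 | 20 | +3 | +2.75 |
| 4 | 19.70 | 20 | 20 | 0 | 0 |
| 5 | 21.83 | 22 | 20 | −2 | −2.14 |
| 6 | 23.58 | 24 | 20 | −4 | −3.88 |
| 8 | 26.33 | 26 | 20 | −6 | −6.63 |
| 10 | 28.47 | 28 | 20 | −8 | −8.77 |
| 12 | 30.21 | 30 | 20 | −10 | −10.51 |

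The unrounded drop exceeds 1 point once creatinine passes 4.0 × exp(0.1/0.957) = 4.44 mg/dL. Reading the table from dialysis back to no dialysis gives the same sizes with the opposite sign.

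**Step 4: other bilirubin and INR values.** The unrounded change is identical, but rounding can move the reported change by a point. At bilirubin 2.0 mg/dL and INR 1.3, the score on dialysis is 25.26 (25). Creatinine 6, 8 and 10 give 29, 32 and 34 off dialysis, so the drops are 4, 7 and 9.

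**Step 5: change from baseline.** The drop appears as a negative change from baseline only if the off-dialysis value above 4.0 mg/dL is the baseline value. If it occurs later, the effect is a false recovery between visits. For example, with bilirubin and INR at 1.0, creatinine 1 at baseline, 8 at a later visit and dialysis after that gives MELD 6, 26 and 20. The changes from baseline are then +20 and +14.

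**Step 6: the 15-point shift table.** The lowest possible MELD at creatinine 4.0 mg/dL is 19.70. The score on dialysis and any off-dialysis score above 4.0 mg/dL are therefore both at least 20 after rounding. The category cannot change through this route.

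**Step 7: with a cap of 4.0 mg/dL off dialysis.** The change on starting dialysis becomes 0 for any earlier creatinine of 4.0 mg/dL or more. Below 4.0 mg/dL it is unchanged from the table. It is never negative at fixed bilirubin and INR.

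**The case against.** The strongest reply is that little depends on this rule. The study tests no hypotheses. MELD is not an event in the Kaplan-Meier analyses, which use hepatorenal syndrome, transplant and death directly. Medians and quartiles are reported beside the means. Creatinine is itself summarised and listed, so a reader could trace an odd MELD value to its cause. The effect also needs creatinine above 4.0 mg/dL off dialysis at one visit and dialysis at least twice in the week before another, with scheduled visits 24 weeks apart. The documents give no frequency for this. All of that stands and keeps the point minor. It does not make the scoring rule consistent.

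A reader might infer three stronger points that the documents do not support:

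- **That small CTP class C cells are distorted.** SAP section 6.1.3.2.3 tabulates MELD change by treatment group. Section 3.2 reserves the CTP-class analyses for progression events and HCC. Section 5.2 summarises MELD by CTP class at baseline only, where no change on starting dialysis can appear.
- **That dialysis is not recorded at all.** It is absent from the protocol's listed assessments, but the SAP also rests on the eCRF, which is not available here. If dialysis were not recorded, the 4.0 rule could never be applied and the drop described here would not arise. That would be a different problem.
- **That every participant scores lower on dialysis.** Below 4.0 mg/dL the score rises on dialysis.

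**Conclusion.** The rule is wrong as written, with limited consequences. For a participant whose off-dialysis creatinine exceeds 4.0 mg/dL, starting dialysis lowers MELD and stopping it raises MELD, with bilirubin and INR unchanged. At the bilirubin and INR floor, the reported drop is 4, 6 or 8 points from creatinine of 6, 8 or 10 mg/dL.

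The affected outputs are individual MELD values, the listing, and the mean, SD, minimum and maximum of MELD and its change from baseline by visit and treatment group. One participant with an 8-point drop shifts the mean in a cell of n participants by 8/n, so overall means probably move little. The minimum or maximum can be set by that one participant.

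Two assumptions carry this: bilirubin and INR are held fixed to isolate the creatinine term, and such participants are taken to be few, which the documents neither confirm nor contradict. It would be a mistake to read the point as undermining the primary endpoint results, since the shift table at 15 and all Kaplan-Meier events are untouched.

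**What to change.** Add one sentence to SAP section 6.1.3.2.3: for all participants, creatinine above 4.0 mg/dL is set to 4.0 in the MELD formula. This uses the SAP's own dialysis value, concerns scoring only, and has no bearing on patient care. Creatinine itself should still be listed and summarised as measured.

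Apply the same rule wherever the score is derived. Protocol section 6.3.9 places the calculation in the clinical database, so changing the analysis programs alone may not be enough. If the database score is kept, its specification needs the same cap; otherwise MELD should be re-derived for analysis from its components.

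The cost is one sentence and a small programming change, with no new data. Because the SAP is already signed, SAP section 1 requires a later change to be documented in the CSR.

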6.2. Secondary Endpoints

The secondary endpoints are:

- The proportion of participants with detectable HCV RNA due to re-emergence of pre-existing virus through Week 240;
- The proportion of participants with detectable HCV resistance mutations through Week 240;

- The proportion of participants with detectable HCV RNA due to re-infection through Week 240.

Virologic relapse is defined as HCV RNA > LLOQ on two samples collected at least one week apart with the same virus present prior to treatment in the parent treatment protocol. Re-infection is defined as HCV RNA > LLOQ on two samples collected at least one week apart with a different virus than that present prior to treatment in the treatment protocol. HCV sequencing will be performed if HCV RNA is sufficient. These results will be listed in CSR by Clinical Virology.

No table will be provided for the secondary endpoints.

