#### 8.1.3. Secondary Endpoints

The secondary endpoints will be assessed in subjects who received their SOF-based regimen in a Gilead parent protocol, as follows:

- The proportion of subjects with detectable HCV RNA due to re-emergence of pre-existing virus through Week 240;
- The proportion of subjects with detectable HCV resistance mutations through Week 240
- The proportion of subjects with detectable HCV RNA due to re-infection through Week 240

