### **8.6.2. Secondary Analyses**

The proportion of subjects with detectable HCV RNA due to re-emergence of pre-existing virus through Week 240 will be summarized by number and percent of subjects by time point using the same model as in the primary analysis.

The proportion of subjects with detectable HCV resistance mutations through Week 240 will be summarized by number and percent of subjects by time point.

The proportion of subjects with detectable HCV RNA due to re-infection through Week 240 will be summarized by number and percent of subjects by time point.

Clinical laboratory test results related to liver disease progression or regression (ie, ALT, AST, bilirubin, albumin, platelets, PT and/or INR, and  $\alpha$ -fetoprotein) will be listed by subject. Reference ranges provided by the laboratory for each parameter will be used to evaluate the clinical significance of laboratory test results. Values falling outside of the relevant reference range will be flagged, as appropriate, in the data listings. Abnormalities in clinical laboratory test results will be summarized by enumeration of the number of subjects with values falling outside of the reference range by study day. Laboratory data will be descriptively summarized over time by study day and by the change from Baseline.

Clinical signs and symptoms related to liver disease progression or regression will be summarized by frequency and percent of subjects. Applicable clinical signs assessed include ascites, hepatic encephalopathy, varices, spontaneous bacterial peritonitis, HCC and transplant. In addition, Child-Turcotte-Pugh score will be included with the following categories, A (5-6), B (7-9), and C (10-15).

Descriptive summaries and listings will be provided for additional efficacy evaluations of the quality of life endpoints.

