3. GENERAL CONSIDERATIONS FOR DATA ANALYSES

Descriptive statistics will be generated for this registry study. For categorical variables, the number and percentage of participants in each category will be presented; for continuous variables, the number of participants (n), mean, standard deviation (SD) or standard error (SE), median, first quartile (Q1), third quartile (Q3), minimum, and maximum will be presented.

By-participant listings will be presented for all participants in the All Enrolled Analysis Set and sorted by participant ID number, visit date, and time (if applicable). Data collected on log forms, such as adverse events (AEs), will be presented in chronological order within the participant. Age, sex at birth, race, and ethnicity will be included in the listings, as space permits.

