3.1.2. Full Analysis Set

The Full Analysis Set (FAS) includes all participants who met all inclusion criteria and did not meet any of the exclusion criteria, and with at least one post-enrollment visit measurement available. We have 34 participants in total enrolled but not included in FAS (32 participants recorded with criteria not met in eCRF and 2 more participants who received PEG/INF in the parent study but without exclusion records in eCRF). This is the primary analysis set for endpoint analyses.

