3.2. Participant Groups

All analyses will be performed and summarized by treatment groups.

Treatment groups are the treatment regimens that led to SVR during the respective parent studies or the treatment regimens received by commercial participants.

For all analyses, treatment regimens will be classified as SOF+RBV, LDV/SOF±RBV, SOF/velpatasvir (VEL)±RBV, SOF/VEL/voxilaprevir (VOX)±RBV, Other, and Total. Details are shown in Appendix 12.3. Participants completing interferon-based regimens such as those with prior treatment being SOF+PEG+RBV will be excluded from the Full Analysis Set and all analyses.

In addition, analyses of events associated with clinical progression of liver diseases and HCC will be performed and summarized by Child-Turcotte-Pugh (CTP) class calculated upon entry into the registry. CTP score will be classified as A (5-6), B (7-9), or C (10-15) in [Table 6-1](#) and [Section 6.1.3.2.3](#).

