6. ENDPOINT ANALYSES

This analysis will be performed after all participants have completed approximately 240 weeks of follow-up or discontinued early from the study.

Primary and secondary endpoints will be summarized on the FAS (Section 3.1.2).

All statistical summaries and analyses will be performed using SAS[®] software (SAS Institute, Cary, North Carolina, USA).

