6.5. Changes from Protocol-Specified Endpoint Analyses

No change from protocol-specified endpoint analysis is planned.

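### SAP 6.2 replaces the protocol's three secondary-endpoint summaries with a listing, while SAP 6 promises a summary and SAP 6.5 declares no change

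*SAP*

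**What the plan says.** Protocol 8.1.3 defines three secondary endpoints, each a proportion through Week 240: detectable HCV RNA from re-emergence of the earlier virus, detectable resistance mutations, and detectable HCV RNA from re-infection. It fixes the population: "The secondary endpoints will be assessed in subjects who received their SOF-based regimen in a Gilead parent protocol". SAP 1.1 repeats that restriction in the secondary objective.

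Protocol 8.6.2 sets the analysis. All three endpoints are to be given as counts and percentages at each time point. Re-emergence "will be summarized by number and percent of subjects by time point using the same model as in the primary analysis", and Protocol 8.6.1 makes that model Kaplan-Meier. Protocol 8.6 adds 95% confidence intervals.

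The SAP deals with these endpoints in three places:

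- SAP 6: "Primary and secondary endpoints will be summarized on the FAS".
- SAP 6.2 restates the three proportions, defines relapse and re-infection, and assigns the results to a listing by Clinical Virology. It ends: "No table will be provided for the secondary endpoints".
- SAP 6.5: "No change from protocol-specified endpoint analysis is planned".

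**The concern.** An endpoint defined as a proportion needs a numerator, a denominator and a time point. A listing of cases gives only the first. If SAP 6.2 is followed as written, the report can describe who had HCV RNA return and what the sequencing showed. It has no planned estimate of how often each cause occurred among the participants to whom the secondary objective applies.

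A SAP may simplify a protocol analysis, and with few events a listing may be a sensible choice. But SAP 6.5 is the section meant to record such a choice, and it records none. A reader who relies on it would believe that the protocol's secondary analyses had been carried through. SAP 6 strengthens that belief by promising a summary that SAP 6.2 then rules out.

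**Working it through.** No figure in the documents needs recalculating. The check sets the sections side by side.

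**Step 1. Planned output for each endpoint.**

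| Secondary endpoint | Protocol 8.6.2 | SAP 6.2 |
|---|---|---|
| Re-emergence | Count and percentage by time point, primary (Kaplan-Meier) model | Listing, no table |
| Resistance mutations | Count and percentage by time point | Listing, no table |
| Re-infection | Count and percentage by time point | Listing, no table |

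Summaries specified in the protocol: 3. Summaries with a planned output in SAP 6.2: 0. Departures declared in SAP 6.5: 0.

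**Step 2. Consistency within the SAP.** SAP 6 commits to summarising primary and secondary endpoints on the FAS. SAP 6.2 rules out a table for the secondary ones, and a by-participant listing is not a summary on an analysis set. The two statements cannot both be carried out.

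**Step 3. Population.** Protocol 8.1.3 and SAP 1.1 both restrict the secondary endpoints to participants treated in a parent study. SAP 6 names the FAS without that restriction. SAP 3.2 shows that the treatment groups also take in "or the treatment regimens received by commercial participants". The intended population is therefore known, but SAP 6 does not carry it into the analysis.

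**Step 4. Can the missing estimates be recovered from other planned outputs?** In part.

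- SAP 6.1.3.1 tabulates cumulative virologic failures, numbers at risk and numbers censored by treatment group and time point. It also lists each failure with parent study, regimen and time to failure.
- SAP 5.1 summarises one variable in non-commercial participants only, which indicates the size of the parent-study subset.
- A reader could therefore combine counts from the virology listing with an approximate denominator and obtain a crude proportion.
- The tabulated risk sets are not restricted to parent-study participants, so the planned tables do not give the Kaplan-Meier estimate for re-emergence.
- The failures in SAP 6.1.3.1 include an unconfirmed last value above the LLOQ. Relapse and re-infection in SAP 6.2 need two samples and a comparison of viruses, with sequencing only where there is enough HCV RNA. The two sets of cases need not match.

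**Step 5. Confidence intervals.** Protocol 8.6 requires them at 95%. SAP 3, 6.1.3.1 and 6.1.3.2.1 itemise the outputs without naming an interval or a method. Nothing in the readable SAP withdraws the requirement. The exploratory sections (SAP 6.3.1 and 6.3.2) are redacted and cannot be checked.

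**The case against.** The strongest case for the plan is that confirmed return of HCV RNA may be rare and that every virologic failure is already listed individually with its parent study, regimen and timing. A case-by-case virology account may then tell the reader more than a table of near-empty cells. No hypothesis is tested, so no decision rests on these proportions. Much of this stands: crude proportions are largely recoverable, and the loss is one of prespecified presentation plus the Kaplan-Meier estimate for re-emergence. It is a reason that could be recorded in SAP 6.5. It does not make the statement of no change true, and it does not reconcile SAP 6 with SAP 6.2.

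Four stronger readings are tempting, and the documents do not support them.

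- A reader might infer that the SAP leaves the secondary population open. SAP 1.1 restates the parent-study restriction, and the relapse definition in SAP 6.2 compares with the virus present before treatment in the parent protocol. The gap is only that SAP 6 does not repeat the restriction.
- A reader might join "By-participant listings will be presented for all participants in the All Enrolled Analysis Set" with "We have 34 participants in total enrolled but not included in FAS" and conclude that ineligible participants enter the secondary results. Neither document says that any of them had HCV RNA above the LLOQ, and SAP 3.2 removes interferon-treated participants from all analyses.
- A reader might infer that the SAP has dropped the 95% intervals. It is silent on them, and silence leaves Protocol 8.6 in force.
- A reader might treat the possible mismatch between the listing and the Kaplan-Meier failures as a contradiction. The two-sample, same-or-different-virus definitions are the protocol's own (Protocol 6.3.2).

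**Conclusion.** The point holds and should be corrected. All three secondary summaries specified in Protocol 8.6.2 are replaced by a listing in SAP 6.2. This conflicts with SAP 6 and makes SAP 6.5 inaccurate. The conclusion rests on readable final text and needs no numerical assumption.

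The consequence is limited to incomplete reporting of a stated secondary objective and an incorrect declaration. It would be wrong to infer bias in the primary results: the analyses of maintained SVR, liver disease progression and HCC do not depend on how the secondary endpoints are presented. The missing confidence-interval method is a one-line clarification, not a second conflict.

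**What to change.** Choose one of two routes.

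1. **Restore the summary.** In SAP 6.2, plan one table in the parent-study participants of the FAS. For each of the three endpoints, give n, percentage and the 95% confidence interval required by Protocol 8.6 at each time point, and add the Kaplan-Meier estimate for re-emergence. For resistance mutations, state the denominator as all parent-study participants in the FAS and show the number sequenced beside it. Amend SAP 6 so that its statement on secondary endpoints carries the same restriction.
2. **Keep the listing and declare it.** Record in SAP 6.5 that the protocol's secondary summaries are replaced by a listing, give the reason, and remove the promise of a secondary summary from SAP 6.

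The SAP file is labelled final and was signed electronically on 10 May 2022. The correction should therefore be made by a SAP amendment or stated in the clinical study report.

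A count of failures that were unconfirmed or not sequenced would help readers relate the table to the virologic failures in SAP 6.1.3.1. It is an optional addition that the protocol does not ask for. One sentence in SAP 3 or 6.1.3 naming the 95% interval and its method for the Kaplan-Meier estimates (for example log-log with Greenwood variance) settles the clarification.

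The cost of the first route is one small table from data already collected, plus a few sentences. Its drawback is sparse cells and wide intervals in small treatment groups. The second route costs only a few sentences.
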